- Not currently using any anti-diabetes medication
- Physically inactive (performing less than two 30 min structured exercise sessions per week for the last year)
- Not pregnant or currently breast feeding
- Pre-menopausal or peri-menopausal
- Not currently involved in a weight loss programme or using weight loss medication

Exclusion Criteria

(Meeting any of the following criteria will prevent you from participating in the study)

- Involved in regular exercise (engaged in more than 3 sessions of structured exercise of $>30 \text{ min}$ per week)
- Currently using anti-diabetes medication (e.g. insulin, metformin)
- Pregnant or breast feeding
- Currently engaged in active weight loss programme or using weight loss medication
- Diagnosed with chronic kidney disease
- Post-menopausal

Plan of investigation

Consent and pre-screening:

Participants will be sent a participant information sheet after expressing interest via email and will have the opportunity to contact with any questions about the study before providing consent via email.

Questionnaire: Participants will complete a Readiness to Exercise questionnaire and send via email to ensure they are fit to undertake exercise as part of the study.

Pre-testing:

Waist-to-hip ratio and weight: Participants will be provided with a tape measure and instructions on how to measure waist circumference and hip circumference. From this, waist-to-hip ratio will be calculated. Additionally, participants will be asked to use their own scales to provide their weight (if they don't have any they will be provided).

Blood pressure: (pending [name] suggestion for this)

Baseline blood sample: Participants will receive blood sample kits containing (Thriva) full instructions that will be used to measure fasting insulin, glucose, lipid profile, HbA1c, cholesterol (includes triglycerides), liver enzymes (ALT usually elevated in people with NAFLD). A researcher will be available to video call if needed while these are being completed.

CGM: Participants will receive a continuous blood glucose monitor that contains full instructions to fit and use. These will be worn for two weeks – 1 week before the intervention and during the first week of the intervention (see Fig. 1).

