Diet: Participants will receive a food diary to record their habitual dietary intake for three days (24 hours after the CGM is fitted). During the first week on the intervention they will also be asked to write down what they eat for lunch on the days they exercise.

Fitness test: Participants will receive a polar beat heart rate monitor and instructions on how to download an app containing a bleep test protocol. They will be asked to complete the bleep test wearing the HR monitor **at least 48 hours before they begin the intervention.**

Exercise intervention:

Pairs of participants from each group (matched for gender, age, BMI and) will be randomized to undertake 12 weeks of steady walking in either a fasted state (before breakfast each day) or a fed state (after breakfast each day). They will be asked to eat the same breakfast on each day they complete the exercise, whether it is before or after.

Walking sessions will be 4 times per week and will be two continuous sessions (~50% HR max) and two interval sessions (3 minutes at 40% HR max, 3 minutes 80% HR max) monitored by the polar beat app. Participants will initially walk for 30 minute sessions in week 1 and this will increase by 5 minutes each week until they are completing 4x 60 minute sessions per week (see table.1).

A CGM will be in place during week 1 to measure the glycaemic response to exercise. And a second CGM will be inserted at the beginning of week 12 to see the changes in glycaemic control on exercise days and will remain in place for post-intervention CGM monitoring.

Post-testing:

The post intervention assessments will be identical in all aspects to the pre-intervention assessments and will begin ≥ 72 hours after the final training session.

Proposed analysis:

Adherence: From the training data, we will monitor adherence to the study intervention since this is remotely ran. We will also monitor whether participants hit their target HR zones during each exercise bout.

Blood samples: All blood samples will be analysed by Thriva.

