CGM: The 24 h glycaemic profile obtained during the CGM period will be used to determine average glucose levels, and the prevalence of hyperglycaemia and hypoglycaemia. Based on the ADA/EASD guidelines, the prevalence of hyperglycaemia and hypoglycaemia will be defined as the total time during which glucose concentrations are >10 mmol.L $^{-1}$ or <3.9 mmol.L $^{-1}$, respectively. The primary outcome from the CGM data will be the time spent in range (3.9 – 10 mmol.L $^{-1}$).

CGM data collection
Pre-testing week
Intervention Week 1
CGM

Day 1	Day 2	Day 3	Day 4	Day 5	Day 6	Day 7	Day 8	Day 9	Day 10	Day 11	Day 12	Day 13	Day 14	Intervention weeks 2-11
Fasting blood samples	Normal diet recorded	Normal diet recorded					Walking session Lunch recorded		Walking session Lunch recorded		Walking session Lunch recorded	Walking session Lunch recorded		

Intervention Week 12
Post-testing week
CGM

Intervention weeks 2-11	Day 1 Walking session Lunch recorded	Day 2	Day 3 Walking session Lunch recorded	Day 4	Day 5 Walking session Lunch recorded	Day 6 Walking session Lunch recorded	Day 7	Day 8 Fasting blood samples	Day 9 Normal diet recorded	Day 10 Normal diet recorded	Day 11	Day 12	Day 13	Day 14
-------------------------	--------------------------------------	-------	--------------------------------------	-------	--------------------------------------	--------------------------------------	-------	-----------------------------	----------------------------	-----------------------------	--------	--------	--------	--------

Figure 1. Plan of CGM data collection. Participants will wear a CGM at two time points; once at the beginning of the study and once at the end. Each CGM time point will measure one resting week and one intervention week.

Table 1. An outline of the walking-based exercise programme. All participants will follow the same intervention make up of 4 sessions per week; 2 continuous walking sessions and 2 interval walking sessions.

Week 1 & 2		Week 7 & 8:	
Session 1: continuous	30 min	Session 1: continuous	45 min
Session 2: Interval	30 min	Session 2: Interval	48 min
Session 3: continuous	30 min	Session 3: continuous	45 min
Session 4: Interval	30 min	Session 4: Interval	48 min
Week 3 & 4:		Week 9 & 10	
Session 1: continuous	35 min	Session 1: continuous	50 min
Session 2: Interval	36 min	Session 2: Interval	54 min
Session 3: continuous	35 min	Session 3: continuous	50 min
Session 4: Interval	36 min	Session 4: Interval	54 min
Week 5 & 6:		Week 11 & 12	

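### The text requires at least 72 h between the last walk and post-testing, but Figure 1 puts the fasting bloods about 48 h after it

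*Protocol*

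**What the plan says.** Under Post-testing, the protocol states that the post-intervention assessments are "identical in all aspects to the pre-intervention assessments" and "will begin ≥ 72 hours after the final training session".

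Under Exercise intervention, participants "will be randomized to undertake 12 weeks of steady walking". The same section adds: "Walking sessions will be 4 times per week". Session length rises "until they are completing 4x 60 minute sessions per week", which Table 1 places in weeks 11 and 12.

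Figure 1 restarts its day numbering for the closing two-week CGM period. In week 12 it shows walks on Days 1, 3, 5 and 6, the last entry reading "Day 6 Walking session Lunch recorded". Day 7 is empty. The post-testing week opens with "Day 8 Fasting blood samples", and diet recording follows on Days 9 and 10.

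Under Pre-testing, the blood kits are "used to measure fasting insulin, glucose, lipid profile, HbA1c" and further analytes. In the opening panel of Figure 1 the baseline bloods fall on Day 1 and the first walk on Day 8.

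**The concern.** The protocol sets an explicit minimum gap between the last exercise session and post-testing, and its own calendar does not deliver that gap for the first post-test item it dates. Bloods are listed under Pre-testing, post-testing repeats the pre-testing assessments, and Figure 1 places the bloods in the post-testing week. Nothing in the protocol exempts them from the 72 h rule.

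Two things are at stake:

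- **Conduct and reporting.** Sampling is done at home with posted kits. Some participants may follow the calendar and others the sentence, and the report could describe a 72 h interval that was not kept.
- **The pre-to-post change.** Baseline bloods precede the first walk, while post-test bloods would come about two days after a 60-minute session. Any short-lived effect of that session on fasting glucose, insulin or lipids would be counted as part of the 12-week change.

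**Working it through.** **Inputs**

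| Input | Value | Source |
|---|---|---|
| Required minimum gap | 72 h | Post-testing |
| Programme | 12 weeks, 4 sessions a week | Exercise intervention |
| Week-12 walks | Days 1, 3, 5, 6 | Figure 1, closing panel |
| Post-test bloods | Day 8 | Figure 1, closing panel |
| Session length in week 12 | 60 min | Exercise intervention; Table 1 |

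**Step 1: is the Day 6 walk the final session?** 12 × 4 = 48 sessions in total. Week 12 holds sessions 45 to 48, drawn on Days 1, 3, 5 and 6. Day 6 is therefore session 48 of 48.

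**Step 2: could the day labels have shifted when the table was extracted?** This is unlikely. In the closing panel each day label stands with its own activity. The opening panel has walks on Days 8, 10, 12 and 13; subtracting 7 gives 1, 3, 5 and 6, the same weekly pattern.

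**Step 3: nominal gap.** (8 − 6) × 24 h = 48 h. Shortfall: 72 − 48 = 24 h.

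**Step 4: largest possible gap.** Count hours from Day 1 at 00:00. A 60-minute walk starting at Day 6, 00:00 ends at (6 − 1) × 24 + 1 = 121 h. Blood at the very end of Day 8 is taken at (8 − 1) × 24 + 24 = 192 h. The gap is 192 − 121 = 71 h, still under 72 h. Counted from the start of the walk it is 192 − 120 = 72 h, but only with a walk at midnight and a sample at midnight. That does not fit walks placed just before or after breakfast, or a fasting sample.

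**Step 5: plausible gap.** The protocol gives no clock times. Assume the walk ends between 07:00 and 12:00 and blood is taken between 06:00 and 10:00:

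- shortest: 48 + (6 − 12) = 42 h
- longest: 48 + (10 − 7) = 51 h

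**Step 6: when is 72 h reached with the walk on Day 6?** On Day 9, at the clock time the walk ended. A walk ending at 08:00 on Day 6 gives 08:00 on Day 9. Bloods on Day 8 precede this at any clock time.

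**Step 7: the other dated items.** The first diet-record day is Day 9: (9 − 6) × 24 = 72 h nominally, although the part of that day before the walk's clock time is under 72 h. The post-testing week of CGM opens on Day 8, so its first day also lies inside the 72 h window.

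**The case against.** The discrepancy itself is hard to dispute; the case on the other side concerns its weight.

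- **Figure 1 is captioned as a CGM plan, and the Post-testing sentence does not cite it.** One could read the sentence as the rule and the figure as a sketch. But the figure is the only calendar in the protocol and it dates the bloods, so anyone scheduling from it would sample too early under the text.
- **The only outcome the protocol calls primary is CGM time in range, not a blood measure.** This stands and limits the consequence. It does not clear the CGM, since that post-testing week opens on Day 8 too. However, the sensor is deliberately in place from the start of week 12, so whether the 72 h rule was meant to govern the CGM window is less clear than for the bloods.
- **Both arms share the same schedule.** This stands. Carry-over common to the arms would largely cancel in the fasted-versus-fed contrast, which is the stated aim. No bias in that contrast has been shown.
- **Baseline may not be exercise-free either.** The fitness test is required only at least 48 h before the intervention and is not dated in Figure 1, so it could precede the Day 1 bloods. The baseline bloods precede the walking programme, but not necessarily all exertion.
- **Changing the calendar has side effects.** Moving the last walk in week 12 alone breaks the match of walk days with week 1. Moving the bloods breaks the match with baseline, where they fall on the first day of the testing week. This is a fair point about the remedy and is taken up there.

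None of this makes the sentence and the figure compatible.

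**Conclusion.** The contradiction holds. The text requires at least 72 h; the calendar gives nominally 48 h for the post-test fasting bloods, 24 h short, and cannot exceed 71 h from the end of the last session. The nominal figure rests only on the days drawn in Figure 1 and the stated session count. The 71 h limit also uses the 60-minute session length and counts from the end of the walk. The 42 to 51 h range rests on assumed morning times.

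The error should be fixed, but it does not threaten the main comparison. It bears mostly on the pre-to-post change in fasting glucose, insulin and lipids, and on the accuracy of the reported interval. The protocol gives neither a reason for 72 h nor a size for any carry-over, so no bias is estimated here and no view is taken on which interval is right.

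**What to change.** Reconcile the Post-testing sentence and Figure 1 before post-testing starts, in one of two ways:

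1. **Change the calendar.** Alter the day of the last walk or the day of the bloods so that the sample falls at least 72 h after the session ends, and move the diet record with the bloods. State the rule in hours, because three calendar days can fall short: with a walk ending at 09:00 and a sample at 07:00 (assumed times), 72 − 2 = 70 h. Say how the change fits the requirement that post-testing mirror pre-testing, and whether week-1 and week-12 walk days still need to match.
2. **Change the sentence.** State the interval actually used, and do not report 72 h.

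In either case, record the end time of the last session and the time of the blood sample, so that the achieved interval can be reported. If the post-testing CGM days are to be analysed as a resting week, state whether the same interval applies to them. When Figure 1 is redrawn, also settle the number of diary days: the Diet section asks for three and the figure draws two at each time point. That is a separate, smaller discrepancy.

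The cost is an edit to one figure or one sentence and to any participant instructions that repeat the schedule. Under the first option the bloods (with the diary) or the last walk move by at least one day, with the loss of day matching noted above. No extra kit is needed.
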